13.3.2 Secondary Outcomes

Analysis for Hypothesis 1b

The number of participants who have a CD4 count ≤350 cells/mm³ and are newly-enrolled in ART within 90 calendar days (i.e., from the date of screening HIV-positive to the date of first receiving ART prescription), will be defined as the numerator for both the One4all Test Intervention and the SOC control groups, separately. The denominator will be defined the number of participants who had a HIV-positive initial EIA screening. Similar to analysis for Hypothesis 1a, random-effect logistic regression will be used to compare the proportion of participants newly enrolled in ART between the two groups.

Secondary Analysis for Hypothesis 1b

The same as the secondary analysis for hypothesis 1a, the outcome variable will not be treated as a binary outcome variable (enrolled in ART within 90 days=1, not enrolled in ART=0) for the secondary data analysis. The time between the initial HIV positive screen by EIA to initiation of ART will be treated as continuous variable (in term of days). HIV-positive participants based on initial screening who did not initiate ART will be censored at the endpoint of the study. Kaplan-Maier and extended Cox model will be used for the data analysis.

Additional Secondary Analysis for Hypothesis 1b

The primary analysis for Hypothesis 1b will be re-calculated with all participants deemed eligible for ART per local hospital provider decision, and would include all participants from the primary Hypothesis 1b analysis (with CD4≤350) with the additional participants with CD4>350 who were recommended for ART by their local providers based on criteria other than CD4. This includes index partners of serodiscordant couples, participants with active tuberculosis, participants with active Hepatitis B, and other conditions summarized in Appendix A. Local providers' decisions on participant ART eligibility will be recorded on study CRFs. Clinical decisions on ART eligibility – particularly for reasons other than CD4 levels - are results of complex decision-marking processes and may vary from provider-to-provider. Note that the focus of this analysis is on the proportion of participants deemed eligible for ART who did initiate ART within the 90 days specified timeframe, and not on the decision-making by the local providers.

Analysis for Hypothesis 1c

The analyses described above (for Hypotheses 1a and 1b) will be repeated by including a predictor variable in the statistical model that is defined by classifying study participants as drug users or non-drug users based on the baseline assessment. This analysis will estimate the association between drug use status at baseline and testing completeness at 1-month follow-up and ART initiation at 3-month follow-up between the One4all Test Intervention and the SOC control groups.

Analysis for Hypothesis 2

The number of participants who have a $VL \le 200$ copies/mL at 12 months will be defined as the numerator for both the One4all Test Intervention and the SOC control groups, separately. The

denominator will be defined as the number of participants who had a HIV-positive initial EIA screening. Similar to analysis for Hypothesis 1a, random-effect logistic regression will be used to compare the proportion of participants virally suppressed between the two groups. Additional descriptive analyses will be performed related to this tertiary outcome, including describing the ART therapy regimen and the adherence to the regimen.

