8.1.2 Secondary Outcome Measures

To maintain consistency with the definitions provided in the CRIMS database, the secondary outcome measure is the proportion of participants with CD4 \leq 350 cells/mm³ who initiate ART within 90 calendar days, defined as starting from the date of initial EIA HIV-positive screening to the date of first receiving ART prescriptions. The denominator is the total number of participants who screened positive on the initial HIV EIA. Participants who are ART-eligible with CD4>350 are included in the denominator but are not included in the numerator for this secondary outcome. An additional secondary analysis will include use of a broader numerator: all participants who are ART-eligible as decided by a local hospital provider based on national treatment guidelines. (**Appendix A**).

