13.1.2 Primary and Secondary Outcomes (Endpoints)

Primary Outcome (Hypothesis 1a)

The primary outcome of this study is the receipt of post-test results and counseling following testing completeness. The numerator is the number of HIV-positive participants who have received post-test results and counseling within 30 days of initial screening blood draw. The denominator is the number of participants who screened positive on the initial HIV EIA in the study arm (control or intervention).

Testing completeness is defined as completion of all three required components: 1) rapid, POC HIV testing, 2) CD4 testing, and 3) confirmatory testing by WB in the SOC or confirmatory testing by VL in the One4all.

The primary endpoint variable (receipt of all post-test results and counseling) will be defined as a binary variable. If an HIV-positive individual has completed and received results on the three required testing components (as defined above) and received post-test counseling within 30 days from his/her HIV screening, it is defined as a complete case, and the variable is defined equal to one. If any test, all three test results, or post-testing counseling are missing, we will define the case as an incomplete case, and the variable is defined equal to zero. Only individuals who have screened positive on the initial EIA will be analyzed. A secondary analysis of the primary endpoint will compare between the two treatment groups time from EIA screening to testing completeness among those who screened HIV-positive on the initial EIA but not restricting to the 30 days period, with those not completing testing censored at the endpoint of the study.

Secondary Outcome (Hypothesis 1b)

A secondary outcome is the proportion of treatment-eligible participants with CD4 \leq 350 cells/mm³ who have initiated ART within 90 days of an initial positive HIV screening. We will define the secondary endpoint variable for Hypothesis 1b as a binary variable. If a participant with CD4 \leq 350 cells/mm³ initiates ART within 90 days of a positive screening, the variable is defined equal to one. Otherwise, the variable is defined equal to zero. All participants who screened HIV-positive on the initial EIA at screening will be included in the analysis.

Secondary Outcome (Hypothesis 1c)

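### Read literally, the time-to-ART analysis of Hypothesis 1b drops the CD4≤350 condition that is part of the endpoint it re-analyses (minor)

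*Protocol*

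**What the plan says.** **Binary endpoint.** Protocol 13.1.2 scores one under this condition: "If a participant with CD4 \leq 350 cells/mm³ initiates ART within 90 days of a positive screening". For everyone else, "Otherwise, the variable is defined equal to zero". The analysis set is all who screened positive on the first EIA: "All participants who screened HIV-positive on the initial EIA at screening will be included in the analysis". Section 8.1.2 settles the case at issue directly: "Participants who are ART-eligible with CD4>350 are included in the denominator but are not included in the numerator for this secondary outcome". The first paragraph of 13.3.2 repeats the numerator: a CD4 count of at most 350 joined to "and are newly-enrolled in ART within 90 calendar days".

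**Time-to-event analysis.** The next paragraph of 13.3.2, the secondary analysis for Hypothesis 1b, announces a change of scale: "the outcome variable will not be treated as a binary outcome variable (enrolled in ART within 90 days=1, not enrolled in ART=0". It defines the new variable thus: "The time between the initial HIV positive screen by EIA to initiation of ART will be treated as continuous variable (in term of days". Its censoring rule is: "HIV-positive participants based on initial screening who did not initiate ART will be censored at the endpoint of the study". Kaplan-Meier and an extended Cox model follow.

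**Broader definition.** A third paragraph of 13.3.2, the additional secondary analysis, re-runs the binary analysis with provider-determined eligibility, adding participants with CD4 above 350 whom providers recommended for ART on other grounds.

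**The concern.** The time-to-event paragraph presents itself as the same outcome on a different scale. Its restated binary variable, its event and its censoring rule all lack the CD4 condition, and the change is not announced. The protocol otherwise keeps the narrow (CD4≤350) and broad (provider-determined) definitions apart, and gives the broad one its own named analysis.

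Participants who start ART with CD4 above 350 are expected. Appendix A lists grounds for treatment at any CD4 level, and 13.3.2 mentions several of them. If they count as events, the hazard ratio filed under Hypothesis 1b answers a wider question than the binary result beside it. Where the two differ, part of the difference would come from the event definition and not from timing.

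**Working it through.** **1. How each rule classifies the same participant** (all are EIA-positive and in both analyses)

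| Participant | Binary 1b (8.1.2, 13.1.2) | Time analysis, literal reading (13.3.2) |
|---|---|---|
| CD4≤350, ART by day 90 | 1 | event |
| CD4≤350, ART after day 90 | 0 | event |
| CD4>350, ART at any time | 0 | event |
| No CD4 result, ART at any time | 0 | event |
| Never starts ART | 0 | censored at study end |

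Row 2 differs because the day limit is lifted, which is intended. Rows 3 and 4 differ because the CD4 condition is missing. The parallel analysis for Hypothesis 1a (13.1.2, 13.3.1) lifts only the 30-day limit and keeps the completion event.

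**2. The plan's own figure, for orientation.** Section 13.2 states 93% power for 14% versus 40%, with ICC 0.082, 6 hospitals of 30 per arm and one-sided alpha 0.05.
- Design effect = 1 + (30 − 1) × 0.082 = 3.378.
- Effective n per arm = 180 / 3.378 = 53.3.
- Unpooled SE = √[(0.14×0.86 + 0.40×0.60) / 53.3] = 0.0822.
- Power = Φ(0.26/0.0822 − 1.645) = 93.5%. With pooled variance under the null it is 92.5%.

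The stated 93% is reproduced. It belongs to the CD4-restricted binary endpoint and is not in question.

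**3. Effect on the day-90 curve.** Censoring is at study end, so under that rule nobody is censored before day 90. One minus the Kaplan-Meier estimate at day 90 is then the crude proportion with an event. On the literal reading it exceeds the binary proportion by the share of the arm that starts ART by day 90 without a CD4 result of at most 350. Step 4 varies only the CD4>350 part.

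**4. Effect on the ratio.** The ratio of cumulative hazards at day 90 is ln(1 − p in One4all) / ln(1 − p in SOC). It equals the hazard ratio if hazards are proportional. With the CD4 condition kept it is ln(0.60)/ln(0.86) = 3.39. The protocol does not give the CD4>350 shares, so those below are assumptions (n = 180 per arm).

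| Added share, SOC / One4all | Day-90 proportion, SOC / One4all | Events, SOC / One4all | Ratio |
|---|---|---|---|
| 0 / 0 | 0.14 / 0.40 | 25.2 / 72.0 | 3.39 |
| 2% / 2% | 0.16 / 0.42 | 28.8 / 75.6 | 3.12 |
| 5% / 5% | 0.19 / 0.45 | 34.2 / 81.0 | 2.84 |
| 10% / 10% | 0.24 / 0.50 | 43.2 / 90.0 | 2.53 |
| 2% / 10% | 0.16 / 0.50 | 28.8 / 90.0 | 3.98 |
| 5% / 15% | 0.19 / 0.55 | 34.2 / 99.0 | 3.79 |
| 10% / 5% | 0.24 / 0.45 | 43.2 / 81.0 | 2.18 |

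Shares of 2 to 15% mean 3.6 to 27 of 180 participants per arm classified in opposite ways. The extreme pairings in that range go further: 15% / 2% gives ln(0.58)/ln(0.71) = 1.59, and 2% / 15% gives ln(0.45)/ln(0.84) = 4.58. The shift can go either way, but every scenario favours One4all.

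**The case against.** The strongest reply is that the paragraph is shorthand. It speaks of the outcome variable just defined. The preceding paragraph also gives the CD4-restricted numerator and then refers loosely to new ART enrolment, and 5.1.2 and 13.6 are equally loose. The protocol says so when it widens the definition, and here it does not. This reading is possible, and it is why a deliberate switch to any ART start cannot be asserted: the protocol never names such an event. But shorthand does not remove the written censoring rule. A participant who starts ART with CD4 above 350 has a start date and does not meet that rule.

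A second reply is that time to any ART start is a legitimate supportive analysis. The synopsis aims to speed ART initiation in eligible patients, eligibility in Appendix A is wider than CD4≤350, and 5.1.2 states the objective without a CD4 limit. That stands, provided the analysis is labelled as such.

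Third, the planned broader binary analysis would partly show how much CD4>350 starts contribute. That also stands, so it would be too strong to say that readers could not separate timing from the change of event.

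Fourth, the SAP, which is not shown, may define the event. Leaving detail to the SAP would be no fault. Here, though, the protocol itself states two rules that conflict when followed as written.

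**Conclusion.** The concern holds as an inconsistency between stated rules: followed literally, the two Hypothesis 1b analyses count different people as events. It is minor, because it concerns a supportive analysis of a secondary endpoint.

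Its size cannot be derived from the protocol. The range of about 2.2 to 4.0 around 3.39 rests wholly on the tabulated assumed shares and on a two-point calculation at day 90. The planned Cox model runs to study end with clustering and covariates, so these are not forecasts of its result.

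A reader might infer that the secondary conclusion could reverse, or that the secondary endpoint is underpowered. The protocol supports neither. The ratio stays above 1 in every scenario computed, the 93% is reproduced for the binary endpoint, and the primary analysis and binary 1b test are untouched.

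**What to change.** In 13.3.2, and in the SAP if it repeats the text:

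- Correct the parenthesis to agree with 13.1.2: one for CD4≤350 with ART within 90 days, zero otherwise.
- Define the event of the Hypothesis 1b time analysis as first ART prescription in a participant with CD4≤350, without the 90-day limit.
- State how an ART start with CD4>350, or with no CD4 result, is handled. Treating it as a competing event and reporting cumulative incidence is one option. It keeps the day-90 estimate in line with the binary proportion.
- Report time to any ART start, labelled as such, as the time-to-event counterpart of the additional secondary analysis.

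The cost is a few sentences, one more curve and one more model. No new data are needed: test results and ART eligibility are on the CRFs (11.2.2), and CD4 results and ART start dates are in CRIMS (16.1). The change should be made before outcome data are compared by arm, so that the event is not chosen with results in view.

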4.1.1 Significance to the Field

Despite the rapid global expansion of ART over the past decade, poor engagement in care for HIV-positive individuals remains a major problem. In order for HIV-positive patients to fully benefit from ART, they need to be aware they are HIV+, be engaged in HIV care, and receive and adhere to their ART regimen.(17) Successful engagement in care is also a precondition for realizing the potential public health benefits of increased ART coverage that may be achieved through the STTR strategy (Figure 2).(18) The STTR strategy is intended to increase engagement in HIV care, and to improve hospital-based HIV testing and treatment services in Guangxi, China. This study endeavors to improve the seek, test and treat portion of the strategy.

Many HIV-positive patients are lost early in the continuum of HIV care due to complicated testing practices. Although HIV screening services are now widely available across China, and HIV provider-initiated testing and counseling (PITC) programs are being rolled out in hospitals in areas of high HIV prevalence, many individuals who screen HIV-positive still do not receive confirmatory testing or are not notified of their results, presenting a first major barrier to accessing HIV care. In Guangxi, site of the planned research, only 50.4% of those who screen HIV-positive receive confirmatory testing, and only 76.0% of those confirmed to be HIV-positive receive their HIV test results (Figure 3). Approximately 31.4% of individuals who are notified of their HIV-positive status fail to receive CD4 testing. Since CD4 level is used to determine ART eligibility, this represents a second major barrier to accessing HIV care. Because of these barriers to ART access, nearly 80% of newly-identified, ART-eligible patients in Guangxi are not engaged in HIV treatment. Application of the new testing algorithm in the One4all Test Intervention will help patients overcome these barriers to treatment, and findings from the research will have direct policy implications in both developed and developing country settings.

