13.2 Rationale for Sample Size and Statistical Power

We have selected a sample size of 180 HIV-positive participants (including approximately 10% DUs) in the control arm and 180 (including approximately 10% DUs) in the intervention arm, across 12 clusters (n=30 individuals in each cluster). This sample will achieve 93% power

based on a one-sided test (alpha=0.05) to detect a difference between the group proportions of 0.28, where under the alternative hypothesis the intervention group proportion is assumed to 0.50 and the control group proportion is assumed to be 0.22. This calculation assumes an intracluster correlation (ICC) within hospitals of 0.082 based on preliminary data. To assess the sensitivity of these calculations based on the 12 clusters and 30 patients per cluster, we examined in the table below effect sizes of 0.28, 0.33, and 0.38 and ICC estimates of 0.072, 0.082, and 0.092, assuming a one-side test at alpha=0.05 and the SOC success rate of 0.22.

		Intra-cluster correlation (ICC)		
		0.072	0.082	0.092
Success rate in One4All	0.50 (delta=0.28)	95.2%	93.6%	92.0%
	0.55 (delta=0.33)	98.8%	98.2%	97.5%
	0.60 (delta=0.38)	99.8%	99.7%	99.5%

Power calculations were also performed for the secondary outcome of initiating ART within 90 days and having a CD4 count \leq 350, among all the HIV-screened positive study participants. Data from preliminary data in Guangxi showed that 14% of HIV screened positive patients had CD4 counts \leq 350 and initiated ART within 90 days. We will have 93% power to detect an increase to 40% in the intervention group of initiating ART with CD4 \leq 350 within 90 days. For these calculations, we used an ICC of 0.082 and a one-sided test at alpha=0.05. All power calculations were performed by the PASS (Version 8) software.

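### The additional ART analysis for Hypothesis 1b has two conflicting descriptions; read literally, Section 13.3.2 compares arms within a subset (those deemed eligible) that the intervention itself changes

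*Protocol*

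**What the plan says.** Section 8.1.2 defines the secondary ART outcome on all screen-positives: "The denominator is the total number of participants who screened positive on the initial HIV EIA". Participants who are ART-eligible with CD4 above 350 "are included in the denominator but are not included in the numerator for this secondary outcome". The additional analysis is then introduced as a change to the numerator alone: "An additional secondary analysis will include use of a broader numerator: all participants who are ART-eligible as decided by a local hospital provider". No new denominator is named.

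Section 13.3.2 repeats the all-screen-positive denominator for the main Hypothesis 1b analysis. Under the additional secondary analysis, it says the main analysis "will be re-calculated with all participants deemed eligible for ART per local hospital provider decision", adding those with CD4 above 350 whom providers recommended for ART on other criteria. It closes with a note that "the focus of this analysis is on the proportion of participants deemed eligible for ART who did initiate ART within the 90 days", as opposed to how providers reached their decisions.

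**The concern.** The two sections give one named analysis two possible estimands: initiators divided by all screen-positives, or initiators divided by those deemed eligible. The second is not protected by the randomisation.

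A participant is deemed eligible only after being assessed, and Section 4.1.1 says CD4 level is used to determine eligibility. Sections 11.2.4, 12.2 and 12.3 show that the arms differ sharply in when that happens. In One4all, CD4 is drawn right after the positive screen, is read in under 30 minutes, and supports a same-day tentative eligibility assessment. Under standard of care (SOC), CD4 is drawn only after the Western blot result has come back and the patient has returned. Another 10–15 days and another recall follow.

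The SOC patients who reach an eligibility decision are therefore those who stayed through several steps, while the One4all group would include many who would have been lost under SOC. Comparing initiation within these two groups sets a selected group against a less selected one. It leaves out the pre-eligibility losses that the testing algorithm is meant to reduce. If the one-tailed 5% test in Section 13.4 were applied here, a selection-driven reversal would read as no benefit and would appear to conflict with the main 1b result.

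**Working it through.** **Inputs from the protocol**
- Section 4.1.1, SOC cascade: 50.4% of screen-positives receive confirmatory testing; 76.0% of those confirmed receive results; "Approximately 31.4% of individuals who are notified of their HIV-positive status fail to receive CD4 testing", so 68.6% of those notified are tested.
- Section 13.2: "Data from preliminary data in Guangxi showed that 14% of HIV screened positive patients had CD4 counts" of 350 or below and started ART within 90 days. The intervention target is 40%, with ICC 0.082, one-sided alpha 0.05, and 6 hospitals of 30 per arm.

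**Reproducing the stated power.** Design effect = 1 + 29 × 0.082 = 3.378. Effective n per arm = 180 / 3.378 = 53.3. For 14% versus 40%, a one-sided z-test gives 93.5% (unpooled variance) or 92.5% (pooled), against the stated 93%. The planning rates are therefore on the all-screen-positive denominator, where the effect is 40 − 14 = +26 points.

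**SOC share reaching a CD4 test.** 0.504 × 0.760 × 0.686 = 0.263.

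**Changing the denominator.** Let c be the share of screen-positives who are CD4-tested and f the share of those tested who are deemed eligible. Then

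initiation among eligible = (initiation among all screen-positives) / (c × f).

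If f is the same in both arms, it cancels from the direction of the comparison. One4all falls below SOC when 0.40 / c(One4all) < 0.14 / 0.263, that is, when c(One4all) > (0.40 / 0.14) × 0.263 = 0.751.

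**Range.** The protocol gives neither f nor the One4all tested share, so both are assumptions here. The difference from SOC, in points, is in brackets.

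| f | SOC | One4all, 70% tested | One4all, 80% tested | One4all, 100% tested |
|---|---|---|---|---|
| 55% | 96.9% | not feasible (over 100%) | 90.9% (−6.0) | 72.7% (−24.1) |
| 60% | 88.8% | 95.2% (+6.4) | 83.3% (−5.5) | 66.7% (−22.1) |
| 70% | 76.1% | 81.6% (+5.5) | 71.4% (−4.7) | 57.1% (−19.0) |
| 80% | 66.6% | 71.4% (+4.8) | 62.5% (−4.1) | 50.0% (−16.6) |

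At f = 60%, the SOC eligible group would be about 180 × 0.263 × 0.60 = 28 people across six hospitals.

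**Sensitivity to the SOC tested share.** The 26.3% treats everyone given a Western blot as confirmed. Applying the Hubei pilot's 282/298 = 94.6% (Section 4.4) gives 24.9% and a threshold of 71.0%. If the SOC share were 35%, the threshold would be (0.40 / 0.14) × 0.35 = 100%, so at 35% or more no reversal can occur under these rates.

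**The case against.** The strongest reply is that no change of denominator was intended. Section 13.3.2 says the main 1b analysis is re-calculated, and that analysis has an explicit all-screen-positive denominator in the same section. The CD4-based group enters the main analysis only through the numerator, so adding provider-determined cases reads naturally as widening the numerator. The protocol also uses the proportion of an eligible group who start ART as shorthand elsewhere: Sections 8.1.2 and 13.1.2 both do so and then place everyone screened positive in the analysis. The closing note in 13.3.2 may only mean that provider decision-making is not under study. This stands as a fair account of probable intent. It does not remove the conflict, because the note, taken as written, describes a proportion of the eligible.

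The arithmetic is also open to challenge, and much of that stands:
- The One4all tested share decides the direction, and the protocol does not give it. Section 12.1 counts patients who leave before hearing their result, and Section 11.2.4 draws CD4 only after at least one further positive rapid test.
- The 14% and 40% cover only initiators with CD4 of 350 or below. The additional analysis is broader, and no rates are given for it.
- The cascade figures and the 14% may come from different data, and equal eligible shares across arms are assumed.
- One4all eligibility on the day is tentative and is re-assessed on the viral load. If the CRF records the final decision, the asymmetry narrows.
- Appendix A lists routes to eligibility at any CD4 level, so CD4 testing is the main gate but not the only one.

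A reader might infer that One4all would look harmful by about 22 points. That figure needs 100% of One4all participants to be tested and a 60% eligible share, and the documents support neither value.

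**Conclusion.** The inconsistency between Sections 8.1.2 and 13.3.2 is real. If 13.3.2 is followed literally, the between-arm comparison is exposed to selection on a status that the assigned arm changes. That bias does not need a reversal to matter.

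Reversal is possible, not established. It rests on the 26.3% SOC tested share, the 14% and 40% planning rates, equal eligible shares in both arms, and more than about 75% of One4all participants being CD4-tested. Within 80–100% tested and eligible shares of 55–80%, the difference is about −4 to −24 points against +26 among all screen-positives.

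It would also be wrong to conclude that the trial loses the benefit it is designed to show. That benefit is testing completeness with results and counselling, and ART uptake is still tested on all screen-positives in the main 1b analysis. Only this additional secondary analysis is affected. Severity is minor to moderate.

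**What to change.** In Section 13.3.2, state both parts of the additional analysis:
- **Numerator:** participants deemed ART-eligible on any provider-determined indication who start ART within 90 days of the initial positive EIA.
- **Denominator:** all participants positive on the initial EIA, as in Section 8.1.2.

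Replace the closing note with a statement that initiation among the deemed eligible is reported by arm descriptively, alongside the number deemed eligible, with no between-arm test. Use the same numerator wording in Section 8.1.2, where the broader numerator is described by eligibility without repeating that ART must have been started. Any SAP text on this analysis should match.

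The cost is wording only. Section 13.3.2 already has provider eligibility decisions recorded on the CRFs, and Section 11.2.2 has ART start dates recorded in CRIMS. No new data and no change to the sample size are needed.
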